 249 team strictly controls access to study data.  
 250

251 All UTHSCSA STRONG STAR network connectivity is segmented with Access Control Lists and is not accessible to any  
 252 other UTHSCSA network segments. STRONG STAR data server is physically located at the Advanced Data Center  
 253 (ADC) has 24x7 onsite security, card key, biometric access controls and video surveillance. University of Texas Health  
 254 Science Center at San Antonio (UTHSCSA) ADC facility also maintains Gen 2 firewall devices to protect and prohibit any  
 255 unauthorized access to UTHSCSA data. All UTHSCSA network devices are monitored by state of the art monitoring  
 256 applications that include configuration audit, management, and availability 24x7.  
 257

258 The UTHSCSA STRONG STAR data server is currently a VMware Instance running Windows Server 2016 Enterprise  
 259 Standard with daily backup services and vSphere Business Continuity Advanced Failover.  
 260

261 Only select Data Core personnel have direct access to the data on a “need to access basis”. Data Core also follows the  
 262 Principals Of Least Privilege (POLP). For example (but not limited to) detecting and repairing data corruption and  
 263 producing reports not currently within the STRONG STAR system. All user activity is tracked and recorded within the  
 264 system so if any records are added, altered or viewed the action is recorded and can be recalled for auditing purposes.  
 265

266  
 267  
 268 **7.3.3. Human Biological Specimen (Biomarker) Processing. N/A**  
 269

270 **7.4 Statistical Consideration**  
 271

272 **7.4.1 Sample Size Estimation.** Following the practice of Schnurr et al. (14) and Monson (15, described in 16), an outcome  
 273 difference of 10 points or more on the CAPS total severity score was chosen as the “non-inferiority margin.” Differences  
 274 smaller than 10 points would be considered clinically insignificant, so non-inferiority will be declared if the upper bound of the  
 275 95% one-sided confidence limit of the difference between group means is less than 10. Schnurr et al. reported the standard  
 276 deviation of the CAPS to be “roughly 20,” so this represents a standardized mean difference in Cohen’s terms (17) of  $d=.50$ , a  
 277 conventional medium effect.  
 278

279 Sample size was determined using the appropriate module for non-inferiority tests in the NCSS/PASS power software  

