 280 (18). Specifications were a 10 point non-inferiority margin, a standard deviation of 20 (14), a true difference between  
 281 treatment groups of zero, one-sided non-inferiority test at  $p=.05$ , desired power=.80 and equal allocation to the two  
 282 treatment groups. With these specifications, PASS reports that N=50 per group is required (note: the same result is given  
 283 by several free online calculators, e.g., <https://www.sealedenvelope.com/power/continuous-noninferior/>;  
 284 <http://powerandsamplesize.com/Calculators/Compare-2-Means/2-Sample-Non-Inferiority-or-Superiority>). As noted in the  
 285 application, this number was increased twice, first by 25% to account for unavoidable loss to follow-up, and then by an  
 286 additional 20% to deal with the as yet unknown psychometric properties of the CAPS-5. This is the basis for proposed  
 287 recruitment of N=175.  
 288

Estimate Required Sample Size	Up to 175
Estimate Participant Screen Out / Drop Out / Withdrawal	30%
Total Enrollment Requirement	275

289  
 290 **7.4.2 Primary (i.e., primary outcome variables) and secondary endpoints.**  
 291

292 The primary treatment outcome variable in this study is PTSD symptom severity, which is assessed using the CAPS-5. The

CAPS-5 will be administered at baseline, 10-, 20-, and 30- weeks following the baseline assessment. The secondary outcome variable is treatment dropout rate for each treatment condition.

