### 7.4.3 Data analysis.

**Hypothesis 1:** Participants randomly assigned to WET will show noninferior outcomes in PTSD symptom severity at the 10-week assessment relative to participants randomly assigned to CPT-C.

**Hypothesis 2:** Participants randomly assigned to WET will show noninferior outcomes in PTSD symptom severity at the 30-week follow-up assessment relative to participants randomly assigned to CPT-C.

We will conduct analyses on both the modified intent to treat (ITT) sample (requiring only attendance at one treatment session) and on the per-protocol (PP) sample of treatment completers. Several authors (e.g., 16, 19) note that PP analysis is an important supplement to the ITT analysis but not a substitute. Although ITT analyses are widely assumed to have a bias in favor of the null hypothesis of no difference, systematic reviews do not always confirm that. Analyses of the PP sample may also be biased, and in either direction. At this point, we believe the consensus in the field is to perform analyses on both ITT and PP samples, and accept the non-inferiority hypothesis only if it is confirmed in both samples.

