Random effects linear (hierarchical linear) models will be implemented for the primary noninferiority ITT randomized comparison of total CAPS-5 score as well as any secondary analyses. This ITT comparison will disregard all CPT-C non-adherence occurring after randomization under the ITT principal (20). The random effects linear models will consist of a random intercept and slope to account for within-patient correlations for the longitudinal observations across follow-up visits (baseline to 10-, 20-, and 30-weeks assessments). Fixed effects specified separately for each post-baseline visit, the intervention, and their respective interactions will be used to obtain the ITT estimate and one-sided 95% confidence interval for the noninferiority test of change from baseline at the 10 week assessment. The test of noninferiority will be based on showing that this upper bound of the one-sided confidence interval is less than the pre-specified margin of 10 CAPS points that is considered to show that WET is noninferior to CPT-C. The 10 week visit will be used to test noninferiority (**Hypothesis 1**), as this would be the first time point of post-treatment for both treatment conditions. Noninferiority will be claimed if the model-based difference between the two conditions is less than this upper bound. The 30 week post-baseline assessment will be used to examine **Hypothesis 2**.

**Hypothesis 3:** WET will have a significantly lower dropout rate relative to CPT-C.

We will conduct survival and logistic regression models to examine treatment dropout rates between the two conditions. The regression models can incorporate predictors (covariate main effects) of dropout, model the timing of attrition, and explore interactions to supplement the primary test of group differences. We will only classify a participant as a dropout if they did not complete the treatment protocol and dropped out of the treatment for reasons other than feeling better and not needing additional treatment.

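### The sentence in 7.4.3 that says when noninferiority is claimed contradicts the plan's own confidence-limit rule and should be aligned with it

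*Combined protocol and SAP*

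**What the plan says.** The plan states the decision rule for noninferiority three times.

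- **Section 7.4.1, Sample Size Estimation:** "so non-inferiority will be declared if the upper bound of the" "95% one-sided confidence limit of the difference between group means is less than 10" (the two quotes run on from each other).
- **Section 7.4.3, Data analysis, random-effects model paragraph:** the test rests on showing that "this upper bound of the one-sided confidence interval is less than the pre-specified margin of 10 CAPS points".
- **Same paragraph, two sentences later:** "Noninferiority will be claimed if the model-based difference between the two conditions is less than this upper bound".

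Section 7.4.3 also says, before the model is described, that the investigators will "accept the non-inferiority hypothesis only if it is confirmed in both samples", meaning the modified ITT and per-protocol samples. On sample size, 7.4.1 reports: "With these specifications, PASS reports that N=50 per group is required".

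**The concern.** The first two statements are the standard noninferiority rule: the upper one-sided 95% limit of the difference must fall below 10. The third is a different rule. In its paragraph the term upper bound refers only to the confidence limit, and the 10 points are called the margin. Taken as written, the sentence sets the model estimate against the upper limit of its own interval. That limit always lies above the estimate, so the condition cannot fail.

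A reader might suppose that the margin was meant. The sentence then sets a point estimate against 10 with no allowance for sampling error, which still conflicts with the other two statements.

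This is the sentence that says when the primary claim will be made. A decision rule is fixed in advance so that it does not depend on interpretation once results are known. Here two incompatible rules stand in one paragraph, and the looser one favours the study hypothesis. The next sentence turns to Hypothesis 2 at 30 weeks without a rule of its own, so the ambiguity can carry over to it.

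**Working it through.** **Inputs, all from 7.4.1:** margin 10, SD 20, true difference 0, one-sided alpha 0.05, power 0.80, equal allocation, 50 per group, recruitment up to 175. A positive difference means that WET does worse.

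**1. Reproduce the plan's sample size under the confidence-limit rule.**

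n per arm = 2 × [(1.645 + 0.842) × 20 / 10]² = 49.5, so 50. This matches the plan. Normal-approximation power at 50 per arm is 0.804. At one-sided 0.025 the same formula gives 62.8, so 63; the stated figure therefore belongs to the one-sided 95% limit.

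**2. Probability of claiming noninferiority under each reading.**

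With SE = SD × √(2/n), true difference d, and Φ the standard normal distribution function:

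- Confidence-limit rule: P(estimate + 1.645 × SE < 10) = Φ((10 − d)/SE − 1.645)
- Estimate against the margin: P(estimate < 10) = Φ((10 − d)/SE)
- Estimate against its own upper limit: P(estimate < estimate + 1.645 × SE) = 1

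At 50 per arm and SD 20, SE = 20 × √(2/50) = 4.00:

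| True WET deficit | Upper limit < 10 | Estimate < 10 | Estimate < own upper limit |
|---|---|---|---|
| 0 | 0.804 | 0.994 | 1.00 |
| 5 | 0.347 | 0.894 | 1.00 |
| 10 | 0.050 | 0.500 | 1.00 |
| 15 | 0.002 | 0.106 | 1.00 |

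At d = 10 the first two rules reduce to Φ(−1.645) = 0.05 and Φ(0) = 0.50. Neither depends on SD or n. No sample size brings the second rule to a 5% error rate, so only the confidence-limit rule fits the plan's alpha and N.

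**3. Results on which the rules disagree.**

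The intended rule passes only if the observed deficit is below 10 − 1.645 × SE. Observed deficits from that threshold up to 10 fail it but pass the estimate-below-10 rule. At SD 20:

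| n per arm | Basis | SE | Threshold | Upper limit if observed deficit is 8 |
|---|---|---|---|---|
| 50 | stated requirement | 4.00 | 3.4 | 14.6 |
| 65.6 | 175 × 0.75 / 2 (assumes 25% loss) | 3.49 | 4.3 | 13.7 |
| 70 | 175 / 1.25 / 2 (reverses a 25% increase) | 3.38 | 4.4 | 13.6 |
| 87.5 | 175 / 2 (full recruitment, no loss) | 3.02 | 5.0 | 13.0 |

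An observed deficit of 8 thus fails the rule in 7.4.1 at every one of these sizes and passes the looser one.

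**4. Sensitivity to the SD.**

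The plan gives no SD for the CAPS-5; one of its sample-size increases is an "additional 20% to deal with the as yet unknown psychometric properties of the CAPS-5". If the SD were 10 (an assumption, for illustration only), the thresholds would be 6.7, 7.1 and 7.5 at 50, 65.6 and 87.5 per arm. The band of disagreement narrows but remains.

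**The case against.** The strongest reply is that nothing of substance is in doubt. The correct rule is stated twice, once in the same paragraph, and the sample size is built on it. The literal reading is vacuous, and nobody would run it as a test. The 50% figure belongs to the other reading, which the text supports less well because it calls 10 the margin. It describes what would happen if an analyst set aside two explicit rules; it is not the expected error rate of this trial. The requirement for confirmation in both samples adds protection. The point-range figures rest on an SD taken from the older CAPS, on a simple two-mean SE in place of the mixed-model SE, and on illustrative sample sizes.

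Much of this stands. The intent is recoverable, the error rates are conditional on following the faulty sentence, and the ranges are illustrations. The 65.6-per-arm row is not a plan figure, and 87.5 per arm is a best case because 175 is a ceiling.

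It does not rescue the sentence. No reading makes it agree with the other two statements, so a reader reaches the right rule only by disregarding it. The both-samples requirement can lower the 50% but does nothing for the literal reading, which passes in both samples. The contrast of 50% with 5% needs no SD, n or choice of SE.

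**Conclusion.** The concern holds. The claim sentence in 7.4.3 is wrong as written and conflicts with 7.4.1 and with the statement two sentences before it. Followed literally, it passes every result. Read as estimate below 10, it gives a 50% false-claim rate at a true deficit of 10, against the planned 5%. These rates are per analysis and assume only an unbiased, approximately normal estimate. The size of the band of affected results depends on the SD and the number analysed; at SD 20 it starts at an observed deficit of 3.4 to 5.0 points and ends at 10.

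This is probably a drafting slip and not a flaw in the design. It should be fixed because it is the operative wording for the primary claim. Whether 10 points suits the CAPS-5, and how 50 per group becomes 175, are separate questions that this conclusion does not touch.

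**What to change.** Replace the sentence with wording such as:

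> WET will be declared noninferior to CPT-C at 10 weeks only when the one-sided 95% upper confidence limit for the model-based difference in change from baseline (WET minus CPT-C, positive values favouring CPT-C) lies below 10 points, in both the modified ITT and the per-protocol analysis.

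The direction of subtraction is an addition. The paragraph does not state it, although the use of an upper limit implies it. The time point and the two-sample condition come from elsewhere in 7.4.3. If the same rule is meant for Hypothesis 2, a clause should say so.

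The cost is one sentence. The model, margin, sample size and trial conduct are unchanged.

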## 358 **8.0 RISKS/BENEFITS ASSESSMENT**

### 359 **8.1 Risks.**

#### 360 **Likely but not Serious (expected to occur in more than 1 in 5 participants):**

- 363 • Possibility of becoming emotionally upset or experiencing an initial increase of PTSD symptoms due to the  
364 discussion or journaling of traumatic events.  
365

#### 366 **Rare and Serious (expected to occur in less than 5 out of 100 participants):**

- 367 • With the handling of medical and research records there is always the possibility of a breach of confidentiality.  
368 However, every effort is made to protect the privacy of participants. Every member of the research team is  
369 carefully trained and monitored about how to store, handle, and protect participant records.  
370

#### 371 **Risks of PTSD Diagnosis regardless of Treatment:**

- 372 • Possibility of increased suicidal risk. One of the risks of PTSD both in and out of treatment is attempted suicide, which  
373 can result in death.  
374

#### 375 **Safeguards for Protecting Participants.**

376  
377 During the early sessions of treatment, participants will be provided immediate coping tools and techniques used to  
378 manage distressing emotions by the study therapist. Distress experienced by participants is expected to be temporary.  
379 Any indication that the participant is considering suicide will be handled following care facility SOPs and using processes  
380 developed by military and civilian consultants to the STRONG STAR Consortium. Trained clinicians and evaluators will  
381 assess history of suicide and current suicidal ideation using the standardized measures such as the Depressive  
382 Symptoms Index – Suicidality Subscale or the Patient Health Questionnaire-9 (PHQ-9) and the Self-Injurious Thoughts  
383 and Behaviors Interview short form. For participants identified as having low to moderate risk for suicide based on the  
384 assessment results, the patient will be maintained on protocol and additional risk management procedures will be  
385 implemented within the context of the study treatment. For participants identified as being at high risk for suicide based on  
386 the assessment results, disenrollment will be considered if it is unlikely that standard treatment plus additional risk  
387 management procedures will maintain safety. High risk participants who are disenrolled from the study will be referred for  
388 more intensive treatment.

389 Risk of loss of identifiable information will be addressed by using unique identifiers for participant data. See above  
390 Section 7.7.2., Data Protection, for further details on protecting data and maintaining confidentiality.  
391

392 Research Monitor: In addition, the study Research Monitor will oversee the safety of the research and report  
393 observations/findings to the IRB or a designated institutional official. The Research Monitor will review all unanticipated  
394 problems involving risks to subjects or others associated with the protocol and provide an independent report of the event  
395 to the IRB. The Research Monitor may discuss the research protocol with the investigators; shall have authority to stop a  
396 research protocol in progress, remove individual human subjects from a research protocol, and take whatever steps are  
397 necessary to protect the safety and well-being of human subjects until the IRB can assess the monitor's report; and shall  
398 have the responsibility to promptly report their observations and findings to the IRB or other designated official and the  
399 HRPO.  
400

401 **8.2 Potential Benefits.** Potential benefits of participation in this study may include a reduction in PTSD symptoms over the  
402 course of therapy. Our primary goal is to treat participants to the point of symptoms reduction below the level of diagnostic  
403 criteria for PTSD. In addition, the knowledge gained from this study will serve to inform the most effective early interventions  
404 for the prevention and treatment of PTSD.  
405  
406

**8.3 Alternatives:** Mental health treatment is available at the San Antonio Military Medical Center at both the Brooke Army Medical Center (BAMC) and at the Wilford Hall Ambulatory Surgical Clinic (WHASC) in San Antonio, TX or the Carl. R. Darnall Army Medical Center (CRDAMC) in Killeen, TX including various forms of psychotherapy and drug treatments. Service Members can request treatment for PTSD through Army One-Source and may be eligible for care at one of the Veterans Healthcare System facilities or clinics. Not participating in the study is also an alternative.

## **9.0 ADVERSE EVENTS, UNANTICIPATED PROBLEMS, AND DEVIATIONS**

**9.1** Adverse Events will be assessed and monitored according to the established STRONG STAR SOP and the treatment facility's policies and procedures.

### **9.2 Reporting Adverse Events, Unanticipated Problems Involving Risks to Subjects or Others (UPIRSOs), and Deviations to the Office of the IRB.**

All adverse events, unanticipated problems involving risk to subjects or others, and deviations will be reported to the Institutional Review Board (IRB) in accordance with current IRB policy. UPIRSOs and recurrent non-compliance with study procedures will be reported promptly to the IRB. Further, the study Research Monitor will review all unanticipated problems involving risks to subjects or others associated with the protocol and provide an independent report of the event to the IRB. All adverse events that do not meet the UPIRSO criteria and deviations that are not non-compliance will be summarized at Continuing Review per the IRB of record's policy.

**10.0 WITHDRAWAL FROM STUDY PARTICIPATION.** Participants may withdraw themselves from this study at any time and for any reason. Withdrawal from this study does not affect the participant's eligibility for care or any other benefits to which entitled. Participants who request to discontinue treatment, but who do not choose to withdraw from the study completely, will be asked to return for the post-treatment assessments. If a participant stops attending treatment sessions without notifying research staff, the therapist or project coordinator will make diligent attempts to contact the person to evaluate their status, attempt to re-engage them in the treatment, and encourage them to complete follow up assessments. Research staff will also refer to appropriate outside resources if necessary. Investigator may choose to withdraw a participant after consultation with the treating therapist and other consultants as appropriate in instances not limited to:

- Patient is noncompliant with treatment requirements
- Patient is in need of more intensive treatment
- Patient's symptoms worsen significantly
- Patient experiences a serious adverse event that is clearly related to the treatment
- Patient becomes actively suicidal
- Unexpected unavailability of a treating therapist

**11.0 USAMRMC Volunteer Registry Database.** We do not anticipate that this will be a greater than minimal risk study necessitating the use of the Volunteer Registry Database will be necessary.

592 PTSD Clinical Trial Award Congressionally Directed Medical Research Program Grant ID: PT140164, PI: [name]

593 **16.0 Description of Assessments:**

- 594
- 595 1. **Demographics and Military Service Characteristics Form.** The Demographics and Military Service  
596 Characteristics Form measures standard demographics (race, gender, age) and military service information (e.g.,  
597 rank).
  - 598 2. **Life Events Checklist for DSM-5 (LEC-5; 21).** The LEC-5 includes the same list of 16 different potentially  
599 traumatic life events from the original LEC that are commonly associated with PTSD symptoms and designed to  
600 facilitate PTSD diagnosis (21). There is also a blank for specifying an additional stressful event not encompassed  
601 in the 16 events. For the CAPS-5, the LEC-5 will be used in identifying the index event and focus of PTSD  
602 treatment. For each potentially traumatic life event, respondents rate their experience of that event on a 6-point  
603 nominal scale (1 = happened to me, 2 = witnessed it, 3 = learned about it, 4 = part of my job, 5 = not sure, and 6 =  
604 doesn't apply). The primary addition to the LEC-5 is a category involving occupational exposure ("for example,  
605 paramedic, police, military, or other first responder"). There has not been a publication on the psychometric  
606 properties of the LEC-5, but the measure is nearly identical to the original LEC. In a group of 108 undergraduate  
607 psychology students the LEC demonstrated good convergence with the Traumatic Life Events Questionnaire  
608 (average kappa = .55) and correlated with the Posttraumatic Stress Disorder CheckList – Civilian version  
609 (reliability coefficients .34 to .48). The LEC demonstrated good test-retest reliability over 7 days (all kappa  
610 statistics except one for "caused serious injury / death of another" > .52). In 131 combat veterans the LEC was  
611 related in the predicted directions with other measures of psychopathology known to be associated with  
612 potentially traumatic life events as assessed with the Posttraumatic Stress Disorder CheckList – Military version,  
613 Clinician-Administered PTSD Scale, and the Mississippi Scale for Combat-Related PTSD. The LEC-5 be  
614 administered at baseline and at 10, 20, and 30-week follow-up assessments.
  - 615 3. **Deployment Risk and Resiliency Inventory-2 (DRRI-2; 27)** Combat Experiences subscale and Postbattle  
616 Experiences subscales. The DRRI-2 is a suite of 17 individual scales that assess key deployment-related risk and  
617 resilience factors with demonstrated implications for veterans' long-term health. The Combat Experiences and  
618 Postbattle Experiences subscales will be administered at baseline to assess stressful deployment experiences.  
619 The DRRI-2 Combat Experiences subscale and Postbattle Experiences subscales will only be administered at  
620 baseline.
  - 621 4. **Clinician Administered PTSD Scale for DSM-5 (CAPS-5; 22).** The Clinician-Administered PTSD Scale (CAPS-  
622 5) is a structured diagnostic interview and gold standard for assessing PTSD. The scale also assesses social and  
623 occupational functioning, dissociation, and the validity of symptom reports. The CAPS was revised to
- 624  
625  
626  
627  
628  
629  
630  
631  
632

accommodate the changes made in DSM-5, to reduce administration time, and to facilitate learning administration and scoring procedures. The CAPS-5 now uses only a single 5-point ordinal rating scale to measure symptom severity. Symptom severity ratings combine information about symptom frequency and intensity obtained by the interviewer. At the same time, the CAPS-5 was revised with an eye towards maintaining backwards compatibility with the DSM-IV version of the instrument. Because the measure is new, psychometrics and diagnostic cutoffs are still being evaluated and there are no formal scoring rules yet. The CAPS-5 will be administered at baseline and at 10, 20, and 30-week follow-up assessments.

5. **PTSD Checklist for DSM-5 (PCL-5; 23).** The PTSD Checklist for DSM-5 is similar in form to the PTSD Checklist (PCL) based on the DSM-IV (24). The PCL-5 is a 20-item self-report measure, selected for its dimensional sensitivity. Scoring is based on how much the patient has been bothered by the symptoms in the past month on a scale from “0 = not at all” to “4 = extremely.” Although extensive empirical testing has not yet been conducted on this measure, initial results suggest that the PCL-5 has psychometric properties commensurate to its predecessor ( $\alpha = .96$  for the total scale;  $\alpha = .84$  test-retest reliability; 25). The PCL will be included in the proposed study to monitor PTSD symptom severity during the treatment phase. The PCL-5 will be administered at baseline, at each treatment session, and at 10, 20, and 30-week follow-up assessments.
6. **Insomnia Severity Index (ISI; 41).** The ISI is a 7-item self-report measure that assesses perceived severity of insomnia. Each item uses a 5-point Likert type scale from 0 to 4, with higher numbers corresponding to greater sleep problems. The items sum to produce a total score (range 0 – 28). The ISI has an internal consistency alpha coefficient of 0.74, and has shown convergent validity with other measures such as the Pittsburgh Sleep Quality Index ( $r = 0.67$ ), the Dysfunctional Beliefs and Attitudes about Sleep ( $r = 0.55$ ), and sleep diaries ( $r$  ranges from 0.32-0.91; 42). This measure will be administered at baseline and at each follow-up.
7. **Snoring, Tired, Observed, Blood Pressure (STOP; 43) Sleep Apnea Screen.** To better understand sleep disturbance associated with PTSD and PTSD treatment, the STOP screen will be administered to screen for sleep apnea. The STOP is a four-item questionnaire developed and validated in 211 pre-operative surgical patients. Based on the endorsement of 2 or more questions, the sensitivity of the STOP ranged from 66% to 80% as compared with the apnea-hypopnea index (AHI) of polysomnography depending upon the AHI cut-off used. Individuals answering “yes” to 2 or more of the questions will be advised that they may be at risk for having sleep apnea and advised that they may want to speak with their primary care provider to consider referral for an overnight sleep evaluation. This measure will be administered at baseline.
8. **Patient Reported Outcomes Measurement Information System (PROMIS) Sleep Disturbance and Sleep-Related Impairment short forms (44).** The PROMIS Sleep Disturbance and Sleep-Related Impairment short forms are self-report measures of past-week sleep disturbance and past-week sleep-related impairment, respectively, derived from the larger PROMIS item banks (45). Each short-form measure includes 8 items, with most items (symptoms) scored in intensity from 1 (“not at all”) to 5 (“very much”). Each measure has shown strong reliability and construct validity (44). This measure will be administered at baseline and at each follow-up.
9. **History of Head Injuries (modified Defense and Veterans Brain Injury Center [DVBIC] 3-Item Screening Tool).** We will use a modified version of the Defense and Veterans Brain Injury Center (DVBIC) 3-Item Screening Tool (46, 47) that was used in STRONG STAR. This instrument, initially called the Brief Traumatic Brain Injury Screen (BTBIS), was used as the gold standard for the diagnosis of TBI in a sample of soldiers returning from duty in Iraq and/or Afghanistan (47). As recommended by the DVBIC, the 3-Question Screen will be considered positive when the participant endorses an injury (question 1) and altered consciousness (question 2, items A-E) for the worst head injury sustained while deployed. The form was modified for STRONG STAR and now CAP to capture the number of injuries, and to answer question 2 based on the worst injury; the original form does not recognize the possibility of multiple head injuries during deployment. As the 3-Question Screen does not query head injuries prior to deployment, an additional four questions have been added to solicit information about each head injury sustained outside of deployment. This measure will be administered at baseline and at each follow-up.
10. **Veterans RAND 12-Item Short Form Health Survey (VR-12).** The VR-12 is a 12-item health questionnaire that was developed from, and explains 90% of the reliable variance of, the longer VR-36 (51). Its items are sampled from each of the eight health domains from the VR-36: physical functioning, role limitations due to physical problems, bodily pain, general health perceptions, energy/vitality, social functioning, role limitations due to

emotional problems, and mental health. Also, there are two summary scales: a physical component summary (PCS) and a mental component summary (MCS). Each item includes a 5-point response scale ranging from “no, none of the time” to “yes, all of the time.” The VR-36 has been widely used, distributed and documented in the Veterans Health Administration. Higher scores indicate better health. This measure will be administered at baseline and at each follow-up.

- 690  
691  
692  
693  
694  
695
- 696 **11. Fagerstrom Test for Nicotine Dependence (FTND; 38).** The Fagerstrom is a 6-item self-report measure that  
697 assesses severity of nicotine dependence. Questions probe both quantity of nicotine use (e.g., number of  
698 cigarettes per day) and pattern of use (e.g., time to first cigarette in morning). Respondents choose among  
699 response options, each of which is assigned a numerical value, with higher numbers corresponding to greater  
700 nicotine dependence. Scores on all items are summed to create a severity index with a range of 0 to 10, with  
701 higher scores indicating more severe dependence. The Fagerstrom scale has been shown to have high  
702 convergent validity with biochemical indices of nicotine use, and the measure has shown acceptable internal  
703 consistency (38). A review of 26 studies of the psychometric characteristics of the Fagerstrom found that it is a  
704 reliable instrument for measuring nicotine dependence in diverse settings and populations (39). This measure will  
705 be administered at baseline and at each follow-up.  
706
- 707 **12. Fagerstrom Test for Nicotine Dependence – Smokeless Tobacco (FTND-ST).** This is a modified version of  
708 the Fagerstrom Test that focuses on smokeless tobacco use, whereas the original Fagerstrom focuses  
709 exclusively on smoking. Like the FTND, the FTND-ST is a 6-item self-report measure of severity of nicotine  
710 dependence that has demonstrated convergent validity with biochemical indices of nicotine use (39, 40). As on  
711 the original FTND, respondents choose among response options, each of which is assigned a numerical value,  
712 with higher numbers corresponding to greater nicotine dependence. Scores on all items are summed to create a  
713 severity index (range = 0–10). This measure will be administered at baseline and at each follow-up.  
714
- 715 **13. Health Questionnaire -** The Health Questionnaire measures medical and mental health diagnoses that  
716 respondents have received, medical board and disability status, medications taken, and caffeine use. The version  
717 of the Health Questionnaires used at follow-ups also probes emergency room use, hospitalizations, mental health  
718 treatments, military status changes, and any important new life events or changes since the time of the last  
719 assessment.  
720
- 721 **14. Mini International Neuropsychiatric Interview (MINI; 26)** is a widely used structured psychiatric diagnostic  
722 instrument. Responses to the interviewer’s questions are rated as either “yes” or “no.” This brief interview (~15  
723 minutes) was validated against the much longer Structured Clinical Interview for DSM-IV. For the proposed study,  
724 the psychotic module of the MINI will be used at baseline to assessment at baseline assessment to determine  
725 study eligibility. The MINI psychotic module will only be administered at baseline.  
726
- 727 **15. Patient Health Questionnaire-9 (PHQ-9; 28).** The PHQ-9 is a widely used and well-validated instrument for  
728 measuring the severity of depressive symptoms. It consists of 9 items that assess both affective and somatic  
729 symptoms related to depression and depressive disorders; these 9 items correspond to the diagnostic criteria for  
730 DSM MDD. Respondents rate the frequency with which they have been bothered by depressive symptoms within  
731 the past two weeks on a scale ranging from 0 (“not at all”) to 3 (“nearly every day”). Scores on all items are  
732 summed to obtain a total severity score. Scores reflect no significant depressive symptoms (0-4), mild depressive  
733 symptoms (5-9), moderate depressive symptoms (10-14), moderately severe depressive symptoms (15-19), and  
734 severe depressive symptoms (>19). Respondents also indicate the degree to which their depressive symptoms  
735 have made it difficult for them to do their work, take care of things at home, or get along with other people, from  
736 “not difficult at all” to “extremely difficult.” The PHQ-9 has high internal consistency (e.g., alpha ranging from .83 to  
737 .92; 29), and correlates strongly with other measures of depression (28). The PHQ-9 will be administered at  
738 baseline, at each treatment session, and at 8, 20, and 30-week follow-up assessments.  
739
- 740 **16. Depressive Symptom Index – Suicidality Subscale (DSI-SS; 48).** The DSI-SS will be used to assess current  
741 suicidal ideation. The DSI-SS is a 4-item self-report measure of suicidal ideation that focuses on ideation, plans,  
742 perceived control over ideation, and impulses for suicide. It is being used as a core measure in the Military  
743 Suicide Research Consortium. Scores on each item range from 0 to 3, with higher scores reflecting greater  
744 severity of suicidal ideation. Instructions will instruct the participants to respond based on the past two weeks. A  
745 systematic review of measures of suicidal ideation and behaviors found that the DSI-SS had evidence of excellent

746 internal consistency and concurrent validity (49). This measure will be administered at baseline and at each  
747 follow-up.  
748

- 749 **17. Self-Injurious Thoughts and Behaviors Interview short form (SITBI; 50).** The SITBI is a structured interview  
750 assessing the historical presence, frequency, and characteristics of self-injurious and suicidal thoughts and  
751 behaviors. The short form version of the SITBI, with 72 items total if no skip-outs are used (i.e., the patient  
752 endorses the initial item in each module), will be administered at baseline by an Independent Evaluator, who will  
753 instruct the participants to answer the questions based on their entire lifetime of experience. The SITBI has shown  
754 high interrater reliability, test-retest reliability, and concurrent validity (50). This measure will be administered at  
755 baseline and at each follow-up.  
756
- 757 **18. Generalized Anxiety Disorder Screener (GAD-7; 30).** The GAD-7 will be used to assess generalized anxiety  
758 symptomology. This is a 7-item measure that asks participants to rate the frequency with which they have been  
759 bothered by anxiety symptoms within the past two weeks on a scale ranging from 0 (“not at all”) to 3 (“nearly  
760 every day”). Scores on all items are summed to obtain a total severity score. Scores reflect no significant anxiety  
761 symptoms (0-4), mild anxiety symptoms (5-9), moderate anxiety symptoms (10-14), and severe anxiety symptoms  
762 (>15). Respondents also indicate the degree to which their anxious symptoms have made it difficult for them to  
763 do their work, take care of things at home, or get along with other people, from “not difficult at all” to “extremely  
764 difficult.” The GAD-7 has been shown to have high internal consistency (e.g.,  $\alpha = .89$ ; 31) and has been shown to  
765 reliably discriminate between anxious and non-anxious diagnostic groups (32). This measure will be administered  
766 at baseline and at each follow-up.  
767
- 768 **19. Alcohol Use Disorders Identification Test (AUDIT; 33) self-report version.** The AUDIT will be used to identify  
769 people with hazardous or harmful patterns of alcohol consumption and to index the severity of these problems. It  
770 will be administered as a self-report form. The AUDIT is a 10-item screening measure, developed by the World  
